12.1 Analysis sets

The analysis sets will be defined for Part 1 and Part 2, respectively.

Part 1:

The Full Analysis Set (FAS) 1 comprises all subjects to whom study treatment has been assigned by randomization in Part 1. According to the intent to treat principle, subjects will be analyzed according to the treatment and strata they have been assigned to during the randomization procedure.

The Safety Set 1 includes all subjects who received at least one dose of study treatment in Part 1. Subjects will be analyzed according to the study treatment received, where treatment received is defined as the randomized treatment if the subject took at least one dose of that treatment or the first treatment received if the randomized treatment was never received.

Part 2:

The Full Analysis Set (FAS) 2 comprises all subjects to whom study treatment has been assigned by re- randomization in Part 2. According to the intent to treat principle, subjects will be analyzed according to the treatment and strata they have been assigned to during the randomization procedure.

The Safety Set 2 includes all subjects who received at least one dose of study treatment in Part 2. Subjects will be analyzed according to the study treatment received, where treatment received is defined as the re-randomized treatment if the subject took at least one dose of that treatment or the first treatment received if the re-randomized treatment was never received.

12.2 Subject demographics and other baseline characteristics

Demographic and other baseline data including disease characteristics will be summarized descriptively by treatment group for FAS 1 and FAS 2, respectively.

Categorical data will be presented as frequencies and percentages. For continuous data, mean, standard deviation, median, 25th and 75th percentiles, minimum, and maximum will be presented.

Relevant medical histories and current medical conditions at baseline will be summarized by system organ class and preferred term, by study part and treatment group.

12.3 Treatments

The Safety set 1 and Safety Set 2 will be used for the analyses below, respectively. Categorical data will be summarized as frequencies and percentages. For continuous data, mean, standard deviation, median, 25th and 75th percentiles, minimum, and maximum will be presented.

The duration of exposure in days to ECF843 and vehiclewill be summarized by means of descriptive statistics.

Concomitant medications and significant non-drug therapies prior to and after the start of the study treatment will be summarized according to the Anatomical Therapeutic Chemical (ATC) classification system, by treatment group.

12.4 Analysis supporting primary objectives

The primary aim of the study is to demonstrate improvement in moderate to severe DED with ECF843. This will be evaluated by measuring signs and symptoms as primary estimands. The analysis of the primary estimands will be based on FAS 1.

12.4.1 Definition of primary endpoint(s)

The two primary endpoints are the change from baseline in SANDE symptom score and the change from baseline in composite corneal fluorescein staining score in Part 1.

12.4.2 Statistical model, hypothesis, and method of analysis

The primary objective of Part 1 of the study is to show that at least one ECF843 arm will improve SANDE symptom score and/or composite corneal fluorescein staining score in comparison with its corresponding vehicle (BID or TID) by rejecting the null hypothesis below at a significance level α =0.05 (2-sided).

H1: $u_T=u_v vs.$ H2: $u_T\neq u_v$

where u_T and u_v are mean change from baseline of SANDE symptom score in ECF843 arm and the corresponding vehicle arm.

H3: $\theta_T = \theta_v vs.$ H4: $\theta_T \neq \theta_v$

where θ_T and θ_v are mean change from baseline of composite corneal fluorescein staining score in ECF843 arm and the corresponding vehicle arm.

Hochberg method will be used to adjust overall type I error (0.05) among the comparisons between each ECF843 arm and its corresponding vehicle for each primary endpoint.

For SANDE symptom score, mixed model repeated measures (MMRM) will be used with change from baseline at all post-baseline score on treatment as response variable, and treatment, day, randomization strata and baseline score as covariates. Two interaction term (treatment*day and baseline*day) will also be included in the model.

For composite corneal fluorescein staining score, MMRM will be used with change from baseline at all post-baseline visits on treatment as response variable, and treatment, visit, randomization strata and baseline score as covariate. Two interaction term (treatment*visit and baseline*visit) will also be included in the model.

For both endpoints, an unstructured within subject correlation structure will be used for covariance matrix. The Kenward-Roger approximation will be used to estimate denominator degree of freedom. Residual/restricted maximum likelihood (REML) method will be used to estimate parameters.

The two-sided p value for the least square mean (LSM) difference between the ECF843 and the vehicle group at each post-baseline day/visit will be reported for the difference.

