- 10.1.1 Adverse events: updated Eye Drop Comfort Scale to be assessed according to new applicable visits:
- 10.1.4 Pregnancy reporting: minor edits to clarify process for pregnancy reporting
- 12.3 Treatments:
- 12.4.2 Statistical model, hypothesis, and method of analysis: type I error control changed from 10% to 5%.
- 12.4.3 Handling of intercurrent events of primary estimand: updated primary estimand strategy.
- 12.4.5 Sensitivity analyses for primary estimand: sensitivity analysis dropped.
- 12.4.6 Supplementary analysis: updated supplementary estimand strategy
- 12.7 Interim Analysis: primary analysis for Part 2 added.
- 12.8 Sample size calculation: sample size adjusted based on updated overall type I error 5%; 95% confidence level provided for updated study design in Part 2.

IRB/ IECs

A copy of this amended protocol will be sent to the Institutional Review Board (IRBs) and Health Authorities.

[figure not shown]
The changes described in this amended protocol require IRB and Health Authority approval, according to local regulations, prior to implementation.

The changes herein affect the trial specific global model consent form.

Protocol sur	
Protocol number	CECF843A2201
Full Title	A randomized, double-masked, multicenter study to evaluate the safety and efficacy of ECF843 vs Vehicle in subjects with dry eye disease
Brief title	A study to assess the safety and efficacy of ECF843 vs Vehicle in subjects with dry eye disease
Sponsor and Clinical Phase	Novartis Phase IIB
Investigation type	Drug; Biological
Study type	Interventional
Purpose and rationale	The purpose of Part 1 of the study is to determine the safety and efficacy of topical ocular ECF843 compared to topical ocular vehicle for the relief of the signs and symptoms associated with moderate to severe dry eye disease (DED).
	Part 2 of the study is intended to explore additional endpoints and potential areas of differentiation as a treatment for patients with DED.
Primary Objective(s)	The primary objective of the study is to demonstrate superiority of ECF843 versus vehicle for improvement in dry eye related ocular symptoms and ocular surface damage as assessed by change from baseline in Symptom Assessment in Dry Eye (SANDE) score and change from baseline in composite corneal fluorescein staining score

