1.2 Purpose

The purpose of the study is to determine the safety and efficacy of topical ocular ECF843 compared to topical ocular vehicle (Part 1) for the relief of the signs and symptoms associated with moderate to severe DED. The study design includes a component for dose-regimen selection. Part 2 of the study is intended to explore additional endpoints and potential areas of differentiation as a treatment for patients with DED.

This Phase II study will establish the foundation for further development and registration of ECF843.

2 **Objectives, endpoints and estimands**

Table 2-1Objectives and related endpoints

Objective(s)	Endpoint(s)	
Primary objective(s)	Endpoint(s) for primary objective(s)	
• Part 1: To demonstrate superiority of ECF843 versus vehicle for improvement in dry eye related ocular symptoms and ocular surface damage	 Change from baseline in Symptom Assessment in Dry Eye (SANDE) score; 	
	Change from baseline in composite corneal fluorescein staining score	
Secondary objective(s)	Endpoint(s) for secondary objective(s)	
 Part 1: To evaluate the improvement of ECF843 vs vehicle in corneal damage by quadrant 	Change from baseline in inferior and central corneal fluorescein staining	
• Part 1: To evaluate the safety of ECF843 vs Vehicle	 Incidence and severity of ocular and non-ocular adverse events 	

2.1 **Primary Estimands**

The estimand is the precise description of the treatment effect and reflects strategies to address events occurring during trial conduct which could impact the interpretation of the trial results (e.g premature discontinuation of treatment).

The primary clinical question of interest is: What is the treatment effect of ECF843 versus vehicle on change from baseline in signs and symptoms in subjects with moderate to severe DED, if artificial tears/gels/lubricants and prohibited medications were not used, and treatment was received for the entire study duration?

The justification for the primary estimands is that they will capture the effect of the study drug for the full duration when administered without confounding effects from prohibited medications or artificial tears/gels/lubricants. Further details can be found in Section 12.

The primary estimands are described by the following attributes:

- 1. Population: subjects with moderate to severe DED. Further details about the population are provided in Section 5.

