2.2 Secondary Estimands

Not applicable.

3 Study design

Figure 3-1 Study Design

The study will be conducted in 2 parts: **Part 1** – efficacy and safety of ECF843 vs vehicle, followed by **Part 2** – additional exploratory assessments of ECF843 vs Vehicle. Both parts of the study include a double-masked study design, with randomization stratified for subjects with Sjogren's Syndrome.

In Part 1 subjects will be randomized to receive twice daily (BID) or three times daily (TID) treatment with either ECF843 or vehicle for 56 days. For subjects randomized to ECF843, the maximum drug exposure will be up to 28 days. At some point during Part 1, all subjects will receive vehicle. The study will be conducted in a way that neither the Investigator nor the subject are aware of the criteria for qualification into the primary efficacy analysis, nor the period(s) during which vehicle treatment is assigned. There will be a database lock after all subjects have completed their participation in Part 1 of the study. The data will be analyzed to determine the efficacy and safety of ECF843 vs vehicle and selection of the optimal concentration and posology. Part 1 must be fully completed prior to initiating Part 2. Part 2 will be initiated only if safety and efficacy of ECF843 during Part 1 is demonstrated.

Between the end of the subject's participation in Part 1 and the beginning of participation in Part 2, subjects will be treated as needed and according to Investigator judgement, and no protocol assessments or proactive solicitation of adverse events will be collected. If a subject spontaneously reports a serious adverse event (SAE) within 30 days of completing Part 1, those events will be captured as stated in Section 10.1.3.

Only subjects assigned exclusively to vehicle treatment in Part 1 may be eligible to participate in Part 2 of the study. A list of subjects eligible for screening in Part 2 of the study will be discussed between the Investigator and the Sponsor prior to initiating screening visits. In the event a study site was initiated close to the end of enrollment and did not have sufficient time to begin recruiting subjects, the site may enroll subjects into Part 2 of the study if approved by the Sponsor.

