12.8 Sample size calculation

12.8.1 **Primary endpoint(s)**

Part 1 of the study is powered on 2 primary endpoints, change from baseline in SANDE symptom score and composite corneal fluorescein staining score.

In one previous rhLubricin clinical study (LUB0114MD) there was an observed standard deviation of 20 mm in change from baseline of SANDE score at Day 28. A second rhLubricin clinical study (LUB0115MD) showed a standard deviation of 23 mm in change from baseline in SANDE symptom score at Day 14.

Assuming a true treatment difference in change from baseline in SANDE symptom score of 10 mm and a standard deviation of 23 mm, a sample size of 112 subjects per arm provides approximately 80% power that the primary analysis will be statistically significant at the two-sided 5% significance level adjusted by 3 comparisons.

See the table below for power to detect a significant difference from vehicle under various assumed treatment effect of SANDE Symptom score and standard deviation.

	Treatment effect: difference from vehicle in change from baseline in SANDE Symptom Score					
Standard deviation of change from baseline in SANDE symptom score	10	11	12	13	14	
23	80%	88%	93%	97%	98%	
25	72%	81%	88%	93%	96%	
27	64%	74%	82%	88%	93%	

 Table 12-1
 Power to Detect a Significant Difference from Vehicle

Assuming a true treatment difference in change from baseline in composite corneal fluorescein staining of 1 and a standard deviation of 1, a sample size of 112 subjects per arm provides more than 99% power that the primary analysis will be statistically significant at the two-sided 5% significance level adjusted by 3 comparisons.

Confidential

nQuery Advisor 8.4 is used for the estimate.

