#### Where

<Dataset> = dataset to store SANDE score or corneal fluorescein staining score where the structure is one record per FAS subject per day/visit.

<Chg> = change from baseline in SANDE score or corneal fluorescein staining score

<Treatment> = randomized treatment assignment

< Sjogren's Syndrome> = diagnosis of Sjogren's Syndrome at baseline

<Visit> = ordered day or visit

Novartis	For business use only	Page 32
SAP		CECF843A2201

<Baseline> = baseline value for SANDE score or corneal fluorescein staining score

The terms in the brackets are to be adjusted according to the real data set and variable names. If an MMRM model (for corneal fluorescein staining score) with unstructured covariance matrix does not converge, choose the covariance structures in the following order until convergence is reached:

- Toeplitz: change to TYPE = TOEP in the 'Repeated' statement;
- First-order autoregressive: change to TYPE = AR(1) in the 'Repeated' statement;
- Compound symmetry: change to TYPE = CS in the 'Repeated' statement.

If an MMRM model (for SANDE score) with Toeplitz covariance matrix does not converge, choose the covariance structures in the following order until convergence is reached:

- First-order autoregressive: change to TYPE = AR(1) in the 'Repeated' statement;
- Compound symmetry: change to TYPE = CS in the 'Repeated' statement.

P-values from three comparisons requested in Section 2.5.1 will be extracted from <Diffs> and adjusted p-values will be calculated using following code:

PROC multtest inpvalues= <rawPvalues> hoc; Run;

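### Part 1 can succeed on either of two primary endpoints, but Hochberg is run within each endpoint at 0.05, so the two-sided familywise error is about 8–9%, not 5%

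*Protocol*

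**What the plan says.** Protocol 12.4.2 sets the Part 1 primary objective as showing that "at least one ECF843 arm will improve SANDE symptom score and/or composite corneal fluorescein staining score" against the matching vehicle, at a two-sided level of 0.05. SAP 2.5.2 repeats this. With three active arms and two endpoints there are six ways to succeed.

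The multiplicity rule in both sections is Hochberg, used to "adjust overall type I error (0.05) among the comparisons between each ECF843 arm and its corresponding vehicle for each primary endpoint". Two other places show that the family is three tests and not six:

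- SAP 5.2.1 describes the code: "P-values from three comparisons requested in Section 2.5.1 will be extracted from" the model output and passed to PROC MULTTEST with the HOC option. SAP 5.2.2 does the same for the supplementary estimand.
- Protocol 12.8.1 and SAP 3.1.1 base power on a result "statistically significant at the two-sided 5% significance level adjusted by 3 comparisons".

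The objective itself is worded differently elsewhere. The protocol summary, Protocol Table 2-1 and SAP Table 1-2 describe it as "To demonstrate superiority of ECF843 versus vehicle for improvement in dry eye related ocular symptoms and ocular surface damage", with *and* in place of *and/or*.

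The result has a direct consequence under Protocol section 3: "Part 2 will be initiated only if safety and efficacy of ECF843 during Part 1 is demonstrated". SAP 1.1.2 adds that at least one concentration and dosing frequency must qualify. Neither document says whether one endpoint is enough.

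**The concern.** Hochberg within an endpoint protects against false positives across the three arms on that endpoint. It does nothing about having two endpoints, each of which can carry the trial alone. The readable text gives no alpha split, no testing order and no rule that both must succeed. The 0.05 attached to the *and/or* objective, and the word *overall* in the Hochberg sentence, therefore promise more than the procedure delivers.

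A reader of the report would take the Part 1 claim as controlled at 5% overall. That claim opens Part 2 and supports the choice of concentration and posology. If the meaning of demonstrated efficacy is left open until the data are seen, the rule can be settled in favour of whichever endpoint won.

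**Working it through.** **Inputs from the documents.** Five arms allocated 1:1:1:1:1 (Protocol 6.1.3). The two TID active arms share the TID vehicle, and the BID active arm has its own (Protocol 4.1). There are 112 subjects per arm. For SANDE the assumed difference is 10 mm and the SD 23 mm; for staining they are 1 and 1 (Protocol 12.8.1). Two-sided alpha is 0.05 (Protocol 12.4.2).

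**Assumption.** The correlation between the two endpoints is not given, so it is varied from 0 to 0.8. One p-value per comparison is assumed.

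**1. The plan's own power figure.** The noncentrality is 10 / (23 × √(2/112)) = 3.254, with 222 degrees of freedom. At alpha 0.05/3 the critical t is 2.412 and power is 79.9%. This agrees with the stated 80%, and all 15 cells of Table 12-1 agree within one point. The sample size was therefore built on a family of three.

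**2. Error by hand.** If each endpoint used its full 5% and the two were independent, the error would be 1 − (1 − 0.05)² = 9.75%. The Bonferroni bound is 0.05 + 0.05 = 10%. Simulation puts Hochberg within one endpoint at 4.8%, so under independence 1 − (1 − 0.048)² = 9.4%.

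**3. Error by simulation.** Global null, 1,000,000 trials per correlation, with two TID contrasts correlated 0.5 through the shared vehicle and the BID contrast independent of them:

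| Endpoint correlation | 0 | 0.3 | 0.5 | 0.8 |
|---|---|---|---|---|
| As written, any two-sided rejection | 9.4% | 9.2% | 8.9% | 7.7% |
| As written, rejections favouring ECF843 only | 4.8% | 4.7% | 4.5% | 3.9% |
| One Hochberg over six, two-sided | 4.8% | 4.7% | 4.6% | 4.0% |
| One Hochberg over six, favouring ECF843 only | 2.4% | 2.4% | 2.3% | 2.0% |
| Both endpoints significant (any arm) | 0.2% | 0.4% | 0.7% | 1.9% |

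At a correlation of 0.7 the as-written two-sided figure is 8.2%, and at 0.9 it is 6.9%.

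**4. What a six-test family costs.** At the strictest step, alpha 0.05/6, the critical t is 2.662 and single-comparison SANDE power is 72.2%. With 129 per arm it is 79.7%, and with 130 it is 80.0%. Because Hochberg is a step-up procedure, the loss depends on what else is significant. SANDE power per active arm (400,000 trials per scenario, stable over correlations 0 to 0.5):

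| True state | Hochberg per endpoint | Hochberg over six |
|---|---|---|
| All doses active on both endpoints | 89% | 89% |
| One dose active on both | 81% | 75% |
| One dose active on SANDE only | 81% | 73% |
| All doses active on SANDE, none on staining | 89% | 76% |

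In the last scenario the chance that at least one arm succeeds on SANDE falls only from 98.6% to about 96.5%.

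**The case against.** The strongest reply is that the Hochberg sentence limits itself. Read to its end, *overall* covers the three arms within one endpoint, and 4.8% is what is delivered there. The code and the power statement agree with that reading. This stands as a coherent account of the procedure. It does not rescue the objective sentence in the same section, which attaches 0.05 to success on either endpoint.

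A second point is that half of the 8–9% consists of findings that ECF843 is worse than vehicle, and these can neither meet the objective nor open Part 2. This is right, and the false-benefit rate of roughly 4–5% is the more relevant figure for decisions. It is still close to double the 2.5% that a two-sided 5% test implies.

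Third, the *and* in the objectives may simply list two domains, with 12.4.2 as the operative rule. That is possible, but the text does not say so, and the error differs greatly between the two readings: 0.2–1.9% against 7.7–9.4%.

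Finally, this is Phase IIb, Part 2 is exploratory, and opening it also requires safety. That limits the consequence. But the plan chose formal hypotheses, a superiority objective and a multiplicity procedure, so its stated error rate should be correct. Redaction does not explain the gap: the multiplicity sentences are intact and agree with each other.

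**Conclusion.** The concern holds. The procedure controls error at 5% within each endpoint, but not for the *and/or* objective to which the plan attaches 0.05. For that objective the two-sided error is about 8–9% for endpoint correlations from 0 to 0.7, and 7.7% at 0.8. It returns to 5% or below only if the endpoints are almost perfectly correlated. The rate of false claims of benefit is 3.9–4.8%. These figures rest on the global null, 112 per arm, one p-value per comparison and the assumed correlation. If both endpoints must succeed there is no inflation, and the fault is then only that 12.4.2 and SAP 2.5.2 state the wrong rule. The analysis remains usable; the point should be fixed before unmasking.

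**What to change.** First, reconcile the two wordings of the objective, and state whether demonstrated efficacy, as the condition for Part 2, means one endpoint or both. If both, say so; no adjustment across endpoints is then needed.

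If either endpoint is enough, choose one of these:

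1. **Control the six tests together.** Pass all six p-values to one PROC MULTTEST HOC call at 0.05, say that control is across the six comparisons, and restate single-comparison SANDE power as 72% to 80%. This takes wording and one line of code. SANDE power per arm is unchanged when staining is significant in all three arms; in the other scenarios above it falls by about 6 to 12 points. No extra patients are needed if that is accepted; restoring 80% at the 0.05/6 step would take 130 analysed subjects per arm instead of 112.
2. **Keep the per-endpoint analysis and describe it correctly.** Delete *overall*, state that 5% applies to each endpoint, and state that the error for the *and/or* objective is up to 10% two-sided, or up to 5% (2.5% + 2.5%) for false claims of benefit. This costs no power and no patients.

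Two other procedures also hold 5%. Hochberg at 0.025 per endpoint gives SANDE power of 73% if one dose is active and 82% if all are. A fixed order within each dose at 0.05/3, staining then SANDE, gives about 80% where staining works, but allows no claim on SANDE alone.
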